the primary owners of a mobile phone with text messaging service, which is anticipated to be at least 75% of parents in this population based on previous research on urban, low-income parents.^{59, 60}

Exclusion criteria: Parents of children with significant medical co-morbidities (e.g., sickle cell disease, insulin-dependent diabetes mellitus) will be excluded because of their increased interaction with healthcare providers.

Recruitment and Randomization

CRA's will identify potentially eligible patients through electronic admission board and medical record diagnostic codes after intake into the ED, and they will describe the study to potentially eligible parents while they are waiting to be seen by a provider. Interested families will be screened for eligibility. If eligible, parents will complete the consent process. (See section 5.2.a for more details.) Then the CRA will administer a baseline questionnaire focusing on health care utilization, asthma self-management and morbidity, parental self-efficacy and outcome expectations. After the questionnaire is completed, participants will be randomized to usual care or the intervention group (T2B). Randomization will occur automatically via the RedCap database system. Time allowing, participants randomized to the intervention will receive brief education on the 3 S's and orientation to the text message component (including an "opt-in" code) while in the ED or if necessary by phone within 48 hours. The text message education component will begin within 1 week after participants are randomized, allowing time for participants to enter the opt-in code.

Retention and Compensation

Parents will receive total compensation of \$110 for participation in the study to be dispensed as: \$20 gift card will be given to the parent after he/she completes the baseline interview and \$30 gift cards will be sent after the 3, 6, 12 follow-up interviews; Based on previous studies conducted by our research team with similar populations, this amount should be sufficient to compensate participants for their time and offset the cost incurred for the text messages (if any), but it will not be coercive, minimizing participation solely based on financial gain.

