In **Aim 2**, we will implement a negative binomial regression model to estimate the IRR and 95% CI for number of follow-up visits with the PCP for asthma care over 12 months in the intervention group compared to the usual care group. In addition to the group variable, the model will include a covariate to account for PCP visit frequency prior to randomization. The exponentiated form of the coefficient of the group term will reflect the relative difference between groups in annual rate of PCP follow-up visits for asthma care. We will use linear regression models to examine the intervention effect on knowledge of self-management (continuous scale score). The model independent variables will include study group and pre-randomization level of knowledge of self-management. The magnitude of the group coefficient will provide an estimate of the size and direction of difference between groups controlling for differences in pre-randomization levels.

We will also assess whether primary care utilization (annual rate of follow-up visits) and increased knowledge of self-management mediate the relationship between the assigned communication intervention and child asthma outcomes (defined as frequency of ED and urgent care visits for asthma care and days of impairment). To do so, we will use path analysis models at baseline and each follow-up time separately. To test these hypotheses using longitudinal data, growth trajectories of each outcome will be modeled using multi-process latent growth models (LGM) of these

proximal and distal outcomes. The hypothesized mediating effects of the proximal outcomes will be tested by relating the intervention condition, the latent slope growth factors of the multiple growth processes, and the distal outcomes.⁸⁶

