In **Aim 3**, we will use linear regression models, as above, to evaluate the intervention effect on measures of self-efficacy and outcome expectations. We will then use path analysis to assess whether parental self-efficacy and outcome expectations (defined using the three validated instruments) mediate intervention effects on PCP follow-up rates and knowledge of self-management. Although the data collected at the 12-month time point will be used as our primary indicator of intervention effectiveness, we will also utilize data collected through the full 24-month follow-up period to evaluate sustainability of the hypothesized effects of the intervention in the same series of analyses. The above analyses estimate the impact of the intervention at observed levels of acceptance of the intervention and thus estimate the expected average effectiveness of the intervention if implemented in a similar population. We will also estimate the magnitude of the effect on each outcome under alternative levels of engagement in the intervention to provide a range of estimated effects based on greater and lesser levels of engagement. Moreover, we will examine potential moderating effects of race/ethnicity on the intervention effects.

C.5.c: Sample Size Estimate

All sample size and power analyses are based on a 2-tailed type 1 error of 5% in final analyses based on 12 month follow-up results. For the primary outcome under **Aim 1** (number of ED visits for asthma care during a 12-month interval), we calculated that a sample size of 125 per study group provides at least 90% power to detect a clinically important 35% reduction in the T2B group compared to the estimated average rate of 1.28 ED visits per year in the usual care group (based on 2012 ED records). For the primary outcome under **Aim 2** (number of PCP visits for asthma care during a 12-month interval), we calculated that a sample size of 120 participants per group provides 90% power to detect an increase to the recommended 3 annual visits in the T2B group over the observed rate of 1.8/year in the previous IMPACT DC sample.⁷ For the other outcomes under Aim 3 (self-efficacy and outcome expectation), a sample size of 85 per group provides 90% power to detect a 0.5 SD effect size difference between study groups. A feasible **analytic sample size of 110** ensures >80% power in all aforementioned analyses.

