In prior studies, we have been able to maintain a 90% retention rate over a 6-month follow-up period. We will employ retention strategies that have been successful in this population in previous studies. Conservatively estimating a retention rate of 80% at the 12-month assessment, we must enroll 138 participants in each group (total N=276). The Seattle Children's ED currently serves approximately 1400 2-12 year old asthma patients per year, 40% (n=530) of whom are Medicaid insured. We estimate that 70% of this total will meet the remaining eligibility criteria (n=371). If 40% of these patients consent to the trial, which is much less than the 60-70% participation rates for Seattle Children's ED-based studies, we will yield our projected sample size of 276 in the proposed 24 month enrollment period. Thus, we estimate that we will need to approach 5-7 parents to recruit at least 3 participants per week, with an estimated recruitment of approximately 12 participants per month (minimum of 6 and maximum of 18 in any given month to assure there is not seasonal over-representation in the study sample).

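### The SAP names no baseline mediator or outcome terms for the H3b path analysis or the follow-up H2c path models, so indirect effects can be biased if T2B shifts the mediator

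*SAP*

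**What the plan says.** **Effect regressions (SAP C.5.b).** The model for PCP follow-up visits has a covariate for visit frequency before randomization. For knowledge of self-management, "The model independent variables will include study group and pre-randomization level of knowledge of self-management". The Aim 3 regressions for self-efficacy and outcome expectations refer back to these models, so they also carry the pre-randomization level.

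**H3b path analysis (Aim 3).** The next sentence reads "We will then use path analysis to assess whether parental self-efficacy and outcome expectations (defined using the three validated instruments) mediate intervention effects", the outcomes being PCP follow-up rate and self-management knowledge. No covariate is named. The 24-month extension repeats the same analyses.

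**H2c path models (Aim 2).** For primary care utilization and knowledge as mediators of child asthma outcomes, "we will use path analysis models at baseline and each follow-up time separately". Baseline thus has its own model. H2c also gets a multi-process latent growth model that relates treatment, slope factors and distal outcomes; H3b does not.

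**Data.** Before randomization, the Protocol (Recruitment and Randomization) administers a "baseline questionnaire focusing on health care utilization, asthma self-management and morbidity, parental self-efficacy and outcome expectations". Under Data Collection, the knowledge questionnaire is given only at baseline and 12 months. Neither document discusses confounding between mediator and outcome.

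**The concern.** T2B is randomized; self-efficacy, outcome expectations, knowledge and PCP use are not. A follow-up path model without baseline values estimates the mediator-outcome path partly from stable differences between families. Parents who start confident may also start knowledgeable and see the PCP more often. If T2B then raises the mediator, the product of the two paths is non-zero even when the mediator does nothing to the outcome.

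The Protocol's background makes a zero baseline association an unsafe default. It reports that self-efficacy was associated with disclosure and question-asking, and that the parent-provider relationship was associated at baseline with fewer prior ED visits. These are not the exact H3b pairs, but they are of the same kind.

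For H2c the sign is uncertain. Sicker children may have both more PCP visits and more ED visits, and that association could hide a protective path.

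At stake is the claim about how T2B works: H3b could be reported as supported on a T2B effect on self-efficacy plus an ordinary pre-existing correlation.

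**Working it through.** **1. Reproduce the plan's figures (SAP C.5.c; two-sided 5% error).** The SAP states that "a sample size of 85 per group provides 90% power to detect a 0.5 SD effect size difference between study groups".
- Normal approximation: n = 2(1.960 + 1.282)² / 0.5² = 84.1, so 85 per group. The t-based power at 85 is 0.900.
- Enrollment: the "analytic sample size of 110" per group and the "retention rate of 80% at the 12-month assessment" give 110 / 0.80 = 137.5, so 138, as stated.

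The documents give no power or error figure for any mediation test.

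**2. Size of the bias.** Let a be the shift in the mediator due to T2B (SD units), r0 the baseline mediator-outcome correlation, and s the baseline-to-follow-up stability of each variable. With unit variances and no true mediator-outcome effect, the unadjusted mediator-outcome coefficient is r0 × s², so

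spurious indirect effect ≈ a × r0 × s².

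For a = 0.5, r0 = 0.3 and s = 0.7: 0.5 × 0.3 × 0.49 = 0.0735 SD. The values of r0 and s are assumptions.

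**3. Simulation.** 2000 trials per cell, 110 per arm, a = 0.5, continuous outcome, and no effect of T2B or mediator on the outcome. Mediation is declared when both paths are significant at 5%.

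| r0 | False mediation, no baseline terms (s = 0.5 / 0.7) | Mean indirect effect, SD (s = 0.5 / 0.7) | False mediation, baseline mediator and outcome in both equations (s = 0.5 / 0.7) |
|---|---|---|---|
| 0 | 4.7% / 5.2% | -0.001 / 0.000 | 4.8% / 4.6% |
| 0.1 | 5.7% / 9.7% | 0.013 / 0.024 | 4.4% / 5.4% |
| 0.2 | 11.1% / 28.5% | 0.024 / 0.048 | 4.6% / 5.3% |
| 0.3 | 20.4% / 55.0% | 0.038 / 0.073 | 4.8% / 4.8% |
| 0.5 | 44.1% / 91.6% | 0.062 / 0.122 | 5.8% / 5.8% |

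Repeat runs agreed to within simulation error. They gave 5% at r0 = 0.1, s = 0.5 and 18% at r0 = 0.3, s = 0.5, which set the lower ends of the ranges quoted in the conclusion.

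**4. Sensitivity of the unadjusted result.**
- a = 0.25: 3% to 43% for r0 from 0.1 to 0.5.
- a = 0: mean indirect effect zero; false mediation at most 4.3%.
- PCP visits as a count with mean 1.8 (the SAP's IMPACT DC rate; assumed between-family spread 0.6 on the log scale), a = 0.5, s = 0.7: 14%, 24% and 57% at r0 = 0.2, 0.3 and 0.5. With baseline terms: 3.9% to 5.1%.
- Reliability 0.70 on all scales (the Protocol's alpha for outcome expectations), a = 0.5, s = 0.7: 16%, 31% and 63%. With baseline terms: 5.4% to 5.8%, with a remaining bias of 0.004 to 0.011 SD.

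**5. What baseline adjustment leaves.** Step 3 makes follow-up residuals independent. If they correlate at ρ, the adjusted indirect effect is about a × ρ. At ρ = 0.1 this is 0.5 × 0.1 = 0.05 SD, and the adjusted model declares mediation in about 30% of trials. At ρ = 0.2 it is 0.10 SD and 83-85%.

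**6. Whether the growth model covers H2c.** Two occasions give 2 means + 2 variances + 1 covariance = 5 moments. A linear growth process needs 2 factor means + 2 factor variances + 1 factor covariance + at least 1 residual variance = 6 parameters. Knowledge, with two waves, therefore cannot be fitted as its own growth process without extra constraints. For measures taken at several waves the model can separate starting level from change, but the text names only slope factors.

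**The case against.** The strongest reply is that the SAP is silent for H3b rather than exclusionary. The path analysis follows directly on regressions that carry pre-randomization levels, and an analyst could reasonably take those terms into the path equations. This stands: a reader might infer that the SAP rules baseline values out, and the text does not say so. But silence permits the biased model. For H2c, fitting each time point separately points more directly to follow-up models without baseline terms. The planned baseline model would reveal the pre-treatment association, but it would not remove it from the follow-up estimates.

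A reader might also infer that these path models are the trial's only evidence on mechanism. They are not: H2c has the growth model, within the limits shown above.

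The high error rates depend on assumed correlations. At r0 = 0.1 the inflation is small, it is lower for counts and for imperfectly reliable scales, and it is absent if T2B does not move the mediator. All of that stands. So does the point that the simulation addresses H3b-type outcomes and puts no figure on H2c, where the bias may run either way.

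Finally, baseline adjustment is not a cure, as step 5 shows. That is a reason to add a sensitivity analysis, not to omit the adjustment.

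**Conclusion.** The concern holds in a conditional form. The SAP specifies baseline terms for its PCP-visit, knowledge and Aim 3 regressions and names none for the H3b path analysis or the follow-up H2c path models. If those models are run without them, T2B shifts the mediator, and mediator and outcome share a lasting baseline correlation, the indirect effect is biased.

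For H3b at the planned 0.5 SD shift with a continuous outcome, false mediation is about 5-10% at r0 = 0.1, 11-29% at 0.2, 18-55% at 0.3 and 44-92% at 0.5, for stability 0.5 to 0.7. For H2c the direction is not known and no magnitude is claimed. The documents do not support saying that spurious mediation will occur, because they give neither r0 nor stability and the T2B effect on the mediators is not yet known.

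Only the mediation hypotheses are touched. The primary ED-visit analysis is unaffected. The change should be made, but it does not bear on the trial's main conclusion.

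**What to change.** Amend SAP C.5.b as follows:

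1. In every H3b path model and every follow-up H2c path model, include the baseline value of the mediator(s) and of the outcome in both the mediator equation and the outcome equation. Models involving knowledge apply at 12 months only.
2. State that indirect effects assume no remaining mediator-outcome confounding after this adjustment.
3. Add a sensitivity analysis that reports the indirect effect over a range of residual mediator-outcome correlations, for example 0, 0.1 and 0.2.

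The baseline questionnaire already covers these domains before randomization, so no new data are needed. The cost is SAP wording, a few degrees of freedom and a little extra analysis.

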enhanced HC intervention to parents of children with other chronic conditions. In addition, the expedience of scaling up a text-message protocol means that our intervention can easily be adapted to reach a broader audience in a cost-effective manner when compared to ongoing face-to-face interventions. If efficacy is demonstrated, another next step will be to expand the program to other healthcare settings, such as primary care practices.

Study Design

We propose to conduct a RCT with low-income parents of children with physician-diagnosed asthma, ages 2-12 years inclusive, who are seen in the Seattle Children's or Mary Bridge Children's ED [for asthma care] to test the efficacy of our mHealth HC intervention, T2B, primarily for reducing ED/urgent care visits for asthma care. Each hypothesis will be tested by contrasting parents receiving T2B with parents receiving only standard ED-based care for their child's asthma, over 12 months.

Study Schedule

Data on child and parent outcomes will be collected in-person at enrollment and by telephone interviews at 3, 6, and 12 months post-enrollment. These telephone interviews will all be coordinated and conducted by the Seattle Children's study staff. Given the highly seasonal nature of asthma-related morbidity, the text message component of the intervention will continue for 12 months (3 months of biweekly educational interactive text messages; ongoing parent-initiated access to key messages and reminder text messages for PCP follow-up/medication refills/annual flu vaccines) allowing for the capture of individual variability in disease course. (Figure 3).

[figure not shown]

Figure 3

Study Population

The study population will be parents/guardians of Medicaid- insured patients seen in the Seattle Children’s or Mary Bridge Children’s ED for treatment of their asthma. These are patients whose asthma is not yet well controlled and who experience the greatest morbidity due to environmental and social factors and are thus the most resource-intensive group.

Inclusion criteria: Parents of Medicaid-insured children age 2 to 12 years inclusive with physician- diagnosed asthma for at least 12 months will be eligible. Older children/adolescents are excluded because they assume greater responsibility for asthma self-management, and their communication with providers becomes more independent over time. Parents must be

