To assist with subject retention, considering the transient nature of this community and the fact that phone numbers are frequently disconnected and/or changed, we will obtain up to 3 contacts' phone numbers from each participant at enrollment, and review and update contacts at each follow-up interview. Using this method in previous studies, our research team has successfully maintained 90% subject retention at 6-month follow-up.¹⁵ In addition, Rip Road has extensive experience working with underserved populations [through public health departments] and pay-as-you-go service providers, and can thus nimbly respond and adapt to

any service interruptions. The window for follow up visits will be two weeks prior and post the due date for the 3 and 6 month follow up time points and 1 month prior and post the due date for 12month follow up time point. To enhance our ability to retain participants for, at each wave of follow-up, the system will send text message reminders to participants to alert them that their follow-up call is approaching and to contact the study coordinator to schedule. If a call has not already been scheduled as of day 1 of the open window, a CRA will contact the family. If no contact has been made as of the due date an online version of the follow up survey will be emailed to the provided email contact. If the participant misses a wave they will still be called for the next follow-up. Information for alternative contacts will also be collected at the time of consent. These contacts will be utilized when participants' provided phone numbers are inactive.

Data Collection

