COVER PAGE

Text2Breathe: Enhance Parent Communication to Reduce Pediatric Asthma Disparities (T2B)

NCT03032159

July 10, 2014

C.5. Statistical Analyses

C.5.a: Preliminary Descriptive Analysis of Data

We will summarize all baseline variables overall and by study arm to assess the balance achieved by randomization and to check assumptions such as normality and equality of variances. The distributions of continuous variables will be summarized using means, standard deviations, medians, and ranges. Categorical variables will be summarized using frequency distributions. Non-parametric tests (e.g., Wilcoxon rank-sum and Fisher's exact) will be used in subsequent analyses as needed. Cronbach alpha reliabilities will be estimated for 12 all standardized instruments to assess whether the instruments are as reliable in our target population as in the population on which the instruments were validated. Frequency of missing data for each outcome variable will be determined at each time point. Baseline characteristics of missing and non-missing respondents at the 3, 6, 12 and 24 month time points will be compared to assess for attrition bias. We will employ multiple imputation to account for missing data, if necessary.^{84, 85} We will examine counts of mobile interactions captured by Rip Road (e.g., number of messages received and sent by each participant; See section 5.1.d.) to assess engagement with the intervention, overall and by participant characteristics.

C.5.b: Analysis Plan for Addressing Specific Aims

In **Aim 1**, to assess the intervention effect on the primary and secondary distal outcomes (i.e., the number of ED visits for asthma care during the 12-month interval following randomization, and the number of days of impairment during the two weeks prior to the 12-month interview, respectively), we will utilize negative binomial regression, a generalization of Poisson regression which yields unbiased inference even if the outcome variable is over-dispersed (i.e., the variance exceeds the mean) to estimate incidence rate ratios (IRRs) and 95% confidence intervals (CIs) for count data. The single independent variable in each model will be study group, and the exponentiated form of its regression coefficient will reflect the relative difference between groups in the annual rate of ED visits or frequency of impaired days.

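### The impairment-days model (Aim 1 secondary outcome, H1b) omits season of enrolment, although each child's two-week window falls near the enrolment anniversary; the cost is precision, not bias

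*SAP*

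**What the plan says.** SAP C.5.b, Aim 1, names two outcomes. The primary is the count of asthma ED visits over the 12 months after randomisation. The secondary is "the number of days of impairment during the two weeks prior to the 12-month interview". Both use negative binomial regression, and "The single independent variable in each model will be study group". By contrast, the Aim 2 models each include the pre-randomisation level of their outcome.

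The protocol (Retention and Compensation) sets the interview window at "1 month prior and post the due date for 12month follow up time point". Its Study Schedule justifies a year-long text programme with the words "Given the highly seasonal nature of asthma-related morbidity".

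The one explicit seasonal rule is in SAP C.5.c, which plans enrolment "with an estimated recruitment of approximately 12 participants per month", with a "minimum of 6 and maximum of 18 in any given month to assure there is not seasonal over-representation in the study sample". The protocol (Recruitment and Randomization) describes automatic randomisation and mentions no stratification by season or calendar time.

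**The concern.** The impairment window closes at the interview, so it lies between about six weeks before and one month after the anniversary of enrolment. A child enrolled in a bad asthma season is therefore assessed in much the same season a year later. If morbidity varies with season, part of the spread in impairment days is explained by a variable that is fixed before randomisation and known for every family, and the model leaves it in the residual.

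The monthly limits do not remove this variation, because they allow three times as many families in one month as in another. Even a perfectly level intake would leave it: families would be spread evenly over the seasons, but season would still add to the spread of the outcome. At stake are the width of the H1b confidence interval and its exposure to a chance difference between arms in when families enrolled.

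**Working it through.** **The plan's own figures.** 110 per arm with 80% retention: 110/0.80 = 137.5, so 138 per arm and 276 in all, as stated. Over 24 months, 276/24 = 11.5 per month, consistent with about 12.

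**What the limits allow.** Six months at 18 and six at 6 give 108 + 36 = 144 per year, a mean of 12 per month, with 108/144 = 75% from half the year. With exactly 276 over 24 months and twelve months at 6, the share is (276 − 72)/276 = 73.9%. If enrolment stops at 276 after twelve months at 18 and ten at 6, it is 216/276 = 78.3%. These are boundary cases.

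**Chance imbalance between arms.** Take a peak-season share p = 0.75 and n = 110 per arm. The standard error of the difference in peak share is √(2p(1 − p)/n) = √(0.375/110) = 0.058, so the 95% range is ±11.4 points. At that limit the shares are 0.807 and 0.693. For a peak to off-peak ratio r, the impairment ratio shifts by (1 + (r − 1)0.807)/(1 + (r − 1)0.693):
- r = 1.5: 1.04
- r = 2: 1.07
- r = 3: 1.10

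This is about 0.2 to 0.6 of the standard error of the log ratio.

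**Precision.** The documents give no seasonal ratio, mean or dispersion for impairment days, so these are assumed: mean 2 to 5 days and negative binomial dispersion k of 1 to 2. With off-peak mean m0 and peak mean m1 = r·m0, averaging μ:
- without season: variance = 2·Var(Y)/(μ²·110)
- with season: variance = 2/(110·[p/(1/m1 + k) + (1 − p)/(1/m0 + k)])

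Example with r = 2, μ = 3, k = 1: m0 = 3/1.75 = 1.714 and m1 = 3.429. The mean of Y² is 22.10, so Var(Y) = 22.10 − 9 = 13.10. Without season the variance is 2 × 13.10/(9 × 110) = 0.0265. With season it is 2/(110 × 0.7385) = 0.0246. The ratio is 0.93, a 7% reduction.

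Reduction in the variance of the log ratio:

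| Assumed ratio | Large-sample formula | Negative binomial simulation | Beta-binomial simulation |
|---|---|---|---|
| 1.5 | 3–4% | none (SD 0.1626 to 0.1632) | 1% |
| 2 | 6–8% | 3% (0.1708 to 0.1679) | 3–5% |
| 3 | 10–14% | 9% (0.1752 to 0.1671) | 9–11% |

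The first two columns use a two-level season. The negative binomial simulation used 1,500 trials per setting, mean 3, k = 1.5, counts capped at 14. The beta-binomial simulation used 8,000 trials per setting, mean 4 of 14 days and correlation 0.35, with sine and cosine of month; there the ratio is peak to trough. Further simulation gave 1%, 4–7% and 11–14%; a smaller run gave 4% at a ratio of 2 and 5–13% at 3. With no seasonality, the two extra terms cost about 1–1.5%.

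**Validity.** Under the null the arms are exchangeable, so omitting season cannot bias the comparison. The negative binomial simulation agrees: type I error without the season term was 3.0%, 4.1% and 4.1% at ratios 1.5, 2 and 3, and the mean log ratio was about 0 (−0.002 to −0.009, against a Monte Carlo error of 0.1752/√1500 = 0.0045 at the largest).

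**The case against.** The strongest reply is that nothing here is wrong, only less efficient than it could be. Randomisation balances season in expectation, the standard error already covers chance imbalance, and H1b is a secondary outcome with no stated power target. That stands, and it limits the point to precision.

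A second reply is that baseline impairment days are collected before randomisation, in nearly the same calendar month as the 12-month interview, and may absorb part of the seasonal variation. That also stands. The gain from season would be somewhat smaller with baseline in the model, and the two have not been compared. But the Aim 1 model contains neither.

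Three stronger readings are tempting, and the documents do not support them.
- **The limits fail to balance the arms.** Their stated aim is the make-up of the sample. Balance between arms is the job of concurrent randomisation.
- **The maximum of 18 endangers accrual.** The SAP's flow is 371 × 0.40 = 148.4 per year, or about 297 in 24 months. If monthly flow varied 3:1 (assumed), the maximum would lower this to 284 and put the chance of missing 276 at 28%. That needs one ED and 40% consent. The SAP reports 60–70% participation in this ED's studies, and the protocol recruits at two EDs. At 1.5 times the flow, the capped totals are about 334–397 and the chance of missing 276 is about 0.
- **The maximum should therefore go.** Removing it would raise seasonal concentration: in the same accrual model at 3:1, the peak-half share goes from 64.0% to 65.5%, or from 58.8% to 65.5% at 1.5 times the flow.

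**Conclusion.** The point holds as a modest loss of precision for H1b. The outcome is tied to season of enrolment by its timing, the protocol recognises the seasonality, the monthly limits leave room for a 3:1 skew, and the model has no term for it. The expected gain from adding season is about 1–4% of the variance at an assumed ratio of 1.5 (one simulation showed none), 3–8% at 2 and 9–14% at 3 (as low as 5% in one smaller run). In the worked example a 7% reduction is equivalent to 110/0.93 = 118 families per arm in place of 110. All of this rests on assumed ratios, means and dispersions.

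A reader might infer that the planned H1b analysis is biased or has inflated type I error. It is not and does not. Nor is the primary outcome exposed in this way: each child's ED count runs for 12 months from randomisation and so covers every season once.

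**What to change.** In SAP C.5.b, Aim 1, pre-specify season of enrolment as a covariate in the impairment-days model, for example sin(2πm/12) and cos(2πm/12) with m the calendar month at randomisation. Ideally add baseline impairment days as well, which would bring the model into line with the baseline adjustment in Aim 2. Keep the exponentiated study-group coefficient and its 95% confidence interval as the effect estimate; with a log link, and no interaction with study group, these terms do not change what the ratio measures. This point requires no change to the ED-visit model or to the monthly limits.

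The cost is SAP wording and two model parameters for season, about 1–2% of precision if there is no seasonality. No new data are needed: the randomisation date is known for every family, and the baseline interview already covers morbidity. The terms should be fixed before outcomes are examined by arm.
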